#### 2 STUDY OBJECTIVES AND ENDPOINTS

#### 2.1 Study Objectives

The primary objective of the study is to assess the safety and tolerability of AGI-134 injected intratumourally, as well as to determine the MTD and the RP2D (in Part 1). Other objectives of this study are to characterise the PK profile of AGI-134 and to support the proposed MoA of AGI-134. Efficacy will be assessed as well by clinical and pharmacodynamic parameters.

# 2.2 Study Endpoints/ Outcomes

# 2.2.1 Primary Endpoints

To assess the safety and tolerability of AGI-134 injected, as well as to determine the MTD and the recommended Part 2 dose (RP2D).

# 2.2.2 Secondary Endpoints

- To characterise the PK profile of AGI-134
- To assess the immune response to AGI-134 and to support the MoA
- To assess biomarkers that may serve as surrogates or predictors of clinical efficacy

# 2.2.3 Exploratory Endpoints

Exploratory endpoints will include the following efficacy endpoints:

[figure not shown]

20		PRIVILEGED & CONFIDENTIAL
Investigational Product: AGI-134		Protocol No. AGI-134.FIM.101
Phase: I/IIa		Version 6.1 31 May 2021

#### 3 STUDY DESIGN

This is a Phase I/IIa, multicentre, two-parts, open-label study, in subjects with unresectable/metastatic solid tumours. The study will be comprised of two parts (Figure 1 and Figure 2):

[figure not shown]
Figure 1: Study Diagram - Part 1

100 E		PRIVILEGED & CONFIDENTIAL
Investigational Product: AGI-134	A Phase I/IIa, multicentre, two-parts, open label study designed to evaluate the safety and tolerability of escalating	Protocol No. AGI-134.FIM.101
Phase: I/IIa		Version 6.1 31 May 2021

Figure 2: Study Diagram - Part 2

# Part 1 - Accelerated Dose Escalation of AGI-134

Part 1 is an accelerated escalation of AGI-134 dose designed to assess the safety and tolerability of AGI-134, as well as to determine the MTD and RP2D.

The total dose will increase incrementally while the concentration will be kept constant at 25 mg/mL, by increasing the total injected volume. A single subject will be administered per dose level beginning with a dose of 25 mg (1 mL) and increasing by 100% to 50 mg (2 mL), to 100 mg (4 mL) and up to a maximal dose of 200 mg (8 mL). The total investigational product volume will be injected in one or more lesions and according to the longest measured dimension of the superficial and/or palpable lesions selected for injection and according to the guidelines presented in the *Administration of AGI-134 and Tumour Biopsy Procedures in Study AGI-134.FIM.101* document. More than one lesion might be injected according to the dose and volume at each escalation level.

At any given dose, if one subject presents with a dose-limiting toxicity (DLT) or an adverse event of moderate or higher severity assessed as related to AGI-134 and as clinically significant during the first cycle of treatment, the group of subjects will be expanded and the study will continue in a conventional "3+3" design. The expansion after an event of moderate severity will be to a total of 3 subjects and the expansion after a DLT will be to a total of 6 subjects, recruited in a stepwise manner of 3+3. Moderate injection-site reactions are expected events with any injectable drug, as are moderate drug administration-related fever, nausea and vomiting. Therefore, these will not be considered as a trigger for conversion to a "3+3" design. If the group of subjects was expanded due to a clinically significant related event that is not a DLT, and this expanded group, i.e. 3 subjects, showed no DLT events, then the study will continue to the next dose level enrolling 3 subjects. If 1 out of 3 subjects presented with a DLT in the expanded cohort, a group of additional 3 subjects will be treated at the same dose level. If no more DLTs

12		PRIVILEGED & CONFIDENTIAL
Investigational Product: AGI-134	A Phase I/IIa, multicentre, two-parts, open label study designed to evaluate the safety and tolerability of escalating	Protocol No. AGI-134.FIM.101
Phase: I/IIa		Version 6.1 31 May 2021

are reported at that dose, i.e. only 1 out of a total of 6 subjects has developed a DLT, the dose escalation will continue to the next level. At any given dose, if 2 or more out of 6 subjects experience a DLT, that dose level will be considered as the DLT dose. In such a case, 3 more subjects will be administered at the previous dose level, if there are less than 6 subjects already treated at that dose. MTD is defined as the highest dose level in which 6 subjects have been administered with and less than 2 instances of DLT.

When the first subject in each dose completes the first cycle of treatment, (each cycle is 3 weeks long), the safety and tolerability will be assessed by a Safety Committee to decide whether to escalate the dose or to expand the group of subjects. When the MTD is reached or the 200 mg dose is found to be safe, whichever comes first, it will be defined as the RP2D and the study will continue to Part 2.

After completion of the first treatment cycle, subjects in Part 1 of the study will continue receiving intratumoural injection at the dose determined at Screening for 3 additional cycles. No intra-subject escalation will be allowed. The treatment regimen is one dose per cycle of AGI-134 every three weeks for up to 4 cycles.

# Part 2- AGI-134 at the RP2D

Protocol AGI-134.FIM.101

This part is designed to assess the safety, tolerability and biological activity of AGI-134 at the RP2D in subjects with either deep or superficial unresectable/metastatic solid tumours. Subjects with selected unresectable/metastatic solid tumours, either superficial or deep lesions, will be enrolled and receive intratumoural injections of AGI-134 according to the injected tumour dimensions in one or more tumours according to the judgement of the PI and the instructions included in the *Administration of AGI-134 and Tumour Biopsy Procedures in Study AGI-134.FIM.101* document, up to, but not exceeding the RP2D at each dosing, every three weeks for up to 4 cycles.

# 3.1 Safety Analysis and Safety Committee

The Safety Committee will be composed of the Study PI, the Sponsor's medical monitor (MM) and Pharmacovigilance associate (PhV) or designee. Ad-hoc members may be invited if needed. The committee will be responsible for the review of all the safety data at pre-defined time points to assess the safety of the therapy. AEs and safety assessments will be monitored throughout the study.

Page 34 of 108

CONFIDENTIAL

<sup>6 Deep lesions are defined as non-palpable lesions, including but not limited to subcutaneous lymph nodes or visceral lesions, injectable with ultrasound or CT guidance. The deep lesions should not be encasing or abutting major vascular structure, e.g., peri-aortic or peri-carotid lesions, or be in a location that is considered high risk for adverse events, e.g., pulmonary parenchyma lesions.

10		PRIVILEGED & CONFIDENTIAL
Investigational Product: AGI-134	A Phase I/IIa, multicentre, two-parts, open label study designed to evaluate the safety and tolerability of escalating	Protocol No. AGI-134.FIM.101
Phase: I/IIa		Version 6.1 31 May 2021

Safety interim analyses will be conducted as follows:

#### Part 1:

- a) At each dose level after the first subject has completed the first treatment cycle.
- b) After 3 subjects have completed the first treatment cycle if the dose level was expanded.
- c) After 6 subjects have completed the first treatment cycle if the dose level was expanded due to a DLT.
- d) Following the first assessment of 3 subjects (or 6 if the dose level was expanded) at each cohort, the SC will meet every 6 months on a regular basis to review ongoing safety data and until the LPLV.

Sites will be required to contact the Sponsor within 24 hours if a subject present with a moderate or severe AE related to AGI-134, that is assessed as clinically significant by the Investigator, during the DLT assessment period (see Section 3.1.1). Mild and moderate injection-site reactions will not be considered as a trigger for conversion to a "3+3" design. Other moderate adverse events that are determined to be not clinically significant by the PI will also not be considered as a trigger for conversion to a "3+3" design (see Section 8.3).

#### Part 2:

- a) After 3 subjects with deep injectable lesions (or 6 subjects, if expansion is needed) have completed the first cycle of treatment with AGI-134 (i.e. Cycle 1/Day 1 through to Day 21).
- b) Every 6 months to review ongoing safety data until the last patient last visit (LPLV).

During this part, 3 subjects will be evaluated after one cycle of injection into a deep lesion. If one or more of the subjects' experiences DLTs, a new assessment will be done after additional 3 subjects with deep lesions injected are enrolled and treated (total of 6 subjects). If no new DLTs are reported, the recruitment will continue as planned. If 2 or more subjects presented a DLT, the Safety Committee will assess the risk vs. benefit of the treatment and recommend whether or not the dose of AGI-134 should be reduced and/or the treatment schedule be changed (see Section 8.3: Ongoing Safety Assessment and Dose-Limiting Toxicity).

### 3.1.1 Ongoing Safety Assessment and Dose-Limiting Toxicity

AEs will be reported from the time of informed consent signature up to 30 days after the last dose of study drug or until the initiation of new anti-cancer treatment, whichever is sooner. SAEs will be reported until 90 days after the last dose of study drug, or until the initiation of new anti-cancer treatment, whichever is sooner. The period considered for DLT assessment for Part 1 is defined as the time from the first dose administration of AGI-134 and up to the end of the first cycle of therapy (i.e. Cycle 1/Day 1 to Cycle 1/Day 21).

agalin A subsidiary of BIG	PRIVILEGED & CONFIDENTIAL
Investigational Product: AGI-134	Protocol No. AGI-134.FIM.101
Phase: I/IIa	Version 6.1 31 May 2021

The period considered for DLT assessment for Part 2 is defined as the time from the first dose administration of AGI-134 and up to the end of the first cycle of therapy (i.e. Cycle 1/Day 1 to Cycle 1/Day 21) for the first 3 subjects with deep lesions.

After the DLT assessment period, data will be assessed on an ongoing basis during the study. All AEs should be captured within the eCRF, however AEs reported beyond the DLT period will not be considered for the DLT assessment.

During Part 2 of the study, any specific AE that fits the DLT definition and occurs at a frequency of > 30% will stop accrual. In this scenario, the Safety Committee may recommend a lower dose level or dosing schedule change for the continuation of the expanded cohort. The study will be discontinued or terminated in case of an unacceptable risk or a negative change in the risk/benefit assessment. This might include the occurrence of adverse events for which character, severity or frequency is unexpected and overcome the potential benefit of the study drug. In addition, any data deriving from other clinical trials or toxicological studies which negatively influence the risk/benefit assessment might cause discontinuation or termination of the study.

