#### Study Design

Moderate injection-site reactions, as well as moderate drug administrationrelated fever, nausea and vomiting, are expected events with any injectable drug; hence these will not be considered as a trigger for conversion to a "3+3" design. If the cohort was expanded due to a clinically significant related event that is not a DLT, and the expanded dose level group, i.e., 3 subjects, showed no DLT events, then the study will continue to the next dose level and enrol 3 subjects. If 1 out of 3 subjects experienced a DLT in the expanded cohort, a group of 3 additional subjects will be treated at the same dose level. If no more DLTs are reported at that dose, i.e., only 1 out of a total of 6 subjects has developed a DLT, the dose escalation will continue to the next dose level that will include 3 subjects. At any given dose, if 2 or more out of 6 subjects experience a DLT, that dose level will be considered as the DLT dose. In such a case, 3 more subjects will be treated at the previous dose level, if there are less than 6 subjects already treated at that dose. MTD is defined as the highest dose level in which 6 subjects have been treated with less than 2 instances of DLT.

When each dose level group completes the first cycle of treatment, (each cycle is 3 weeks long), the safety and tolerability will be assessed by a Safety Committee (SC) to decide whether to escalate the dose or to expand the dose level group. When the MTD is reached or the 200 mg dose (the highest dose proposed to be tested) is found to be safe, whichever comes first, it will be defined as the Recommended Part 2 Dose (RP2D) and the study will continue to Part 2.

After completion of the first treatment cycle, subjects in Part 1 of the study will continue receiving intratumoural injections at the dose determined at Screening for 3 additional treatment cycles. No intra-subject escalation will be allowed. The treatment regimen is one dose of AGI-134 per cycle; each cycle is 3 weeks long. The duration of the cycle may be extended if needed to complete additional safety evaluations. Dosing will be given for up to 4 cycles.

98		PRIVILEGED & CONFIDENTIAL
Investigational Product: AGI-134	A Phase I/IIa, multicentre, two-parts, open label study designed to evaluate the safety and tolerability of escalating	Protocol No. AGI-134.FIM.101
Phase: I/IIa	doses of AGI-134 in unresectable/metastatic solid tumours.	Version 6.1 31 May 2021

	 
yê -	T.

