# Ongoing Safety Assessment and Dose-Limiting Toxicity

AEs will be reported from the time of informed consent signature Up to 30 days after the last dose of study drug or until the initiation of new anticancer treatment, whichever is sooner. SAEs will be reported until 90 days after the last dose of study drug, or until the initiation of new anticancer treatment, whichever is sooner.

agalin A subsidiary of Bit	OLINERX	PRIVILEGED & CONFIDENTIAL
Investigational Product: AGI-134		Protocol No. AGI-134.FIM.101
Phase: I/IIa	doses of AGI-134 in unresectable/metastatic solid tumours.	Version 6.1 31 May 2021

Study Assessments	The period considered for DLT assessment is defined for Part 1 and Part 2, as the time from the first dose administration of AGI-134 and up to the end of the first cycle of therapy (e.g., Cycle 1/Day 1 through to Cycle 1/Day 21).  After the DLT assessment period, data will be assessed an ongoing manner during the study. All AEs should be captured within the eCRF; AEs reported beyond the DLT period will not be considered for the DLT assessment.
	General instructions before study drug administration
	The following instructions should be followed before AGI-134 administration:
	
 
AGI-134 should only be administered when personnel and therapies are immediately available for the treatment of hypersensitivity reactions, should they occur. This should include having an open IV cannula and fluid therapy readily available.
 

	
 
Hypovolaemia, if present, should be corrected prior to administration of AGI 134 according to the study site standard of care.
 

	
 
For patients who receive routine anti-hypertensive medication, these medications should be withheld in the 24 hours prior to injection of AGI-134.
 

	Recommendations for patients who experience systemic reactions related to study drug are detailed in section 5.7.
Study	The duration of core study participation is 54 weeks.
Duration	A Termination visit will be performed for all subjects on Week 54. Long-term follow-up will continue for all subjects for up to 5 years.
	The study consists of the following study periods:
	Screening Period: up to 28 days
	Core Study: up to 54 weeks
	Long-Term Follow-Up: Following Termination/Early Termination visit, a follow-up telephone call will be performed to all subjects every 9 weeks up to 5 years in order to assess duration of response and survival.
Planned	Part 1: Up to 24 subjects.

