## 5.3 Core Study

The duration of the Core Study will be up to 54 weeks.

AGI-134 administration is divided into cycles (each cycle is 3 weeks long). Each cycle may be extended if additional safety assessment is needed.

AGI-134 is administered for up to 4 cycles. For administration and tissue biopsies information and guidance, please refer to the instructions in the *Administration of AGI-134 and Tumour Biopsy Procedures in Study AGI-134.FIM.101* document.

Visits will be named as follows:

- AGI-134 Administration Visits: Visit Cycle 1-Day 1, Visit Cycle 2-Day 1, Visit Cycle 3-Day 1, Visit Cycle 4-Day1
- Other Visits:
   Visit Cycle 1-Day 3, Visit Cycle 1-Day 8, Visit Cycle 1-Day 15, Visit Week 18,
   Visit Week 27, Visit Week 36, Visit Week 45, Week 54 (Termination)

## 5.3.1 Cycle 1

This visit will begin after completion of the Baseline visit. Treatment initiation may be done on the same day of Baseline visit, but Baseline procedures should be completed prior to investigational product administration. On this day, AGI-134 will be administered. The following activities will be performed during this visit. Details on the specific days for each assessment are presented in the SoA (APPENDIX A).

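### The ±3-day window on Cycle 2 allows dose 2 on Days 19–21, inside the 21-day DLT period, and the protocol states no explicit numeric minimum dose interval

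*Combined protocol and SAP*

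**What the plan says.** **DLT period.** Section 3.1.1 runs the period "up to the end of the first cycle of therapy (i.e. Cycle 1/Day 1 to Cycle 1/Day 21", for Part 1 and for the first deep-lesion subjects in Part 2. Section 8.3 gives the same span for the escalation. The synopsis has "up to the end of the first cycle of therapy (e.g., Cycle 1/Day 1 through to Cycle 1/Day 21", with Day 21 as an example rather than a definition.

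**Dosing and cycle length.** The synopsis (Study Design) states: "The treatment regimen is one dose of AGI-134 per cycle; each cycle is 3 weeks long". Section 5.3.4 places the injection on Day 1 of each of Cycles 2 to 4. Section 5.3, which covers both parts, adds: "Each cycle may be extended if additional safety assessment is needed". Nothing provides for a shorter cycle. For Part 1, Section 3 continues: "After completion of the first treatment cycle, subjects in Part 1 of the study will continue receiving intratumoural injection"; Section 8.3.1 repeats this. For Part 2, Section 3 gives only a three-weekly frequency.

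**Decisions tied to the first cycle.** In Part 1 a qualifying event triggers expansion if it occurs "during the first cycle of treatment, the group of subjects will be expanded". The Safety Committee chooses between escalating and expanding "When the first subject in each dose completes the first cycle of treatment".

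**Visit windows.** Tables 6 and 7 each carry a scheduling-window row that is a default, giving way where something else is specified. Both give Cycle 2 ±3 days. Both use a one-sided +3 for the Cycle 1 Day 8 and Day 15 visits. The AGI-134 administration row has an entry under Cycle 2 in both tables, and its footnote sets no interval between doses.

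**Separate document.** Section 5.3 says: "For administration and tissue biopsies information and guidance, please refer to the instructions in the" administration and biopsy procedures document. That document is not part of the material reviewed.

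**The concern.** The default window lets dose 2 fall before the DLT period has run its 21 days. Part 1 is a first-in-human escalation that starts with one subject per level and doubles the dose at each step. The first cycle of that one subject is the main evidence for the next step. If dose 2 arrives on Days 19–21, the last days of the period no longer show the effect of dose 1 alone, and a reaction on those days has two candidate doses.

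In Part 2 the stake is narrower: the safety check on the first 3 deep-lesion subjects (6 if expanded). The RP2D has been set by then.

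**Working it through.** This is calendar arithmetic; no sample-size formula applies.

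**Inputs**
- Cycle length: 3 weeks (synopsis, Study Design; Section 5.3).
- DLT period: Cycle 1 Day 1 to Day 21 (Sections 3.1.1 and 8.3).
- Dosing on Day 1 of each cycle (Section 5.3.4; Table 7 footnote).
- Cycle 2 window: ±3 days (Tables 6 and 7).

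**Step 1: the plan's own figure.** 3 × 7 = 21 days, so Cycle 1 is Days 1–21, which matches the stated DLT period.

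**Step 2: nominal dose 2.** Day 1 + 21 = Day 22, the first day of week 4. This agrees with Table 7, which places Cycle 2 in weeks 4–6.

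**Step 3: apply the window.** Day 22 − 3 = Day 19 and Day 22 + 3 = Day 25. Dose 2 is allowed on Days 19–25, a dose interval of 18 to 24 days. Days 19, 20 and 21 lie inside the DLT period.

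**Step 4: observation on dose 1 alone.** Days = min(21, day of dose 2 − 1).

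| Dose 2 on | Days on dose 1 alone | Share of 21 |
|---|---|---|
| Day 19 | 18 | 85.7% |
| Day 20 | 19 | 90.5% |
| Day 21 | 20 | 95.2% |
| Day 22 or later | 21 | 100% |

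The largest loss is 3/21 = 14.3%. These are shares of days in the worst permitted cases, not probabilities.

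**Step 5: look for an overriding rule.**
- The footnotes to Tables 6 and 7 set specific timings for ECG, vital signs, PK samples and biopsies, but none for the interval between doses.
- Section 6.7.4 limits how late treatment may resume after an interruption, not how early the next dose may be given.
- The Part 1 text in the synopsis, Section 3 and Section 8.3.1 puts further injections after completion of the first cycle. With a 3-week cycle that can only be extended, this implies Day 22 or later without stating a day.
- The Part 2 text has no such after-completion sentence. The general 3-week cycle in Section 5.3 still applies.

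Part 1 therefore has a conflict between table and text. Part 2 has a plainer gap.

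**Step 6: how an event on Days 19–21 would be classed.** Section 8.3.3 counts a qualifying toxicity that occurs after at least one dose and within the DLT period. With the period ending on Day 21, a reaction on Day 20 after an early dose 2 meets both conditions and would most naturally count. The effect is an extra DLT of uncertain attribution, not a missed one.

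**Step 7: with a 0/+3 window.** Dose 2 falls on Days 22–25, an interval of 21 to 24 days, and observation on dose 1 alone is always 21 of 21 days.

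**The case against.** The strongest reply is that the protocol already settles this for Part 1. The window row is only a default. The body text fixes a 3-week cycle, mentions only extension, and places later injections after the first cycle is complete. On that view the text overrides the table, and dose 2 cannot precede Day 22. This stands as an account of intent, and it rules out the claim that nothing in the protocol bears on the timing. It does not remove the conflict. The Part 1 text gives no day count, sites book visits from the table, and the Part 2 text is weaker.

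A second reply concerns Table 6. In the extracted text each cycle has one window entry for three day columns, so applying ±3 to the Day 1 dosing column is an inference. That is fair for Part 1. In Table 7 Cycle 2 is a single column and the window sits directly over the dosing row.

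Third, the administration document might set a minimum interval. That cannot be checked here.

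A reader might go further and infer that an early dose 2 ends Cycle 1, so that an escalation step rests on an 18-day DLT period and dose-2 reactions drop out of the count. The synopsis wording and the tie to the first cycle give this some colour. The documents do not support it as an equal reading. Sections 3.1, 3.1.1, 8.3 and 8.3.2 fix the end at Day 21 as a definition, and a period ending on Cycle 1 Day 21 presupposes that Cycle 1 has a Day 21.

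**Conclusion.** The point holds as an inconsistency of minor severity. Read literally, the Cycle 2 window permits dosing on Days 19–21, inside the DLT period. In Part 1 this contradicts the text; in Part 2 the text says too little to prevent it. No explicit numeric minimum dose interval appears in the protocol.

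The consequence is up to 3 fewer days on dose 1 alone, and unclear attribution of an event on Days 19–21. Because such an event would most naturally count as a DLT, the error runs in the cautious direction: it could prompt an expansion or add to the DLT count at a level, but would not hide toxicity. It would be wrong to conclude that the MTD or RP2D is unsound. The problem needs early-edge dosing, and a consequence for the DLT count also needs a qualifying event by Day 21. The Safety Committee reviews all safety data, and adverse events after the DLT period are still captured.

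This rests on two assumptions: that the ±3 entry in Table 6 covers the dosing day, as it does in Table 7, and that the administration document sets no minimum interval.

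**What to change.** Add one footnote to the AGI-134 administration row in each of Tables 6 and 7: for DLT-evaluable subjects, Cycle 2 Day 1 dosing has a 0/+3 window, with dose 2 no earlier than Day 22. DLT-evaluable means all Part 1 subjects and the first 3 deep-lesion subjects in Part 2 (6 if expanded). All other visits keep their windows. If the administration document already sets a minimum interval, the footnote should agree with it.

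The cost is two footnotes and the loss of up to 3 days of early-side flexibility at one visit. The tables already use a one-sided +3 window in Cycle 1, so the format is familiar to sites. The DLT definition, the escalation rules and the sample size do not change. The footnote does not deal with a first cycle that is extended beyond 21 days, which is a separate matter. This is a cheap improvement.
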